### 7.2 NULL AND ALTERNATIVE HYPOTHESES

No confirmatory hypothesis testing is planned. This study is considered exploratory.

### 7.3 PLANNED ANALYSES

The analysis populations are defined below. Patients will be analyzed according to randomized treatment, unless otherwise specified. Important protocol violations and the handling of patients with such violations will be described in the TSAP.

#### **Treated Set (TS)**

The Treated Set will consist of all patients who were treated with at least one dose of trial drug (BI 1467335 or placebo).

#### **Full Analysis Set (FAS)**

The FAS will consist of all the patients who were randomized, treated with at least one dose of BI 1467335/placebo and have baseline and one on-treatment DRSS assessment.

#### 7.3.1 Primary endpoint analyses

No primary efficacy endpoint has been defined for this study.

For analyses of the primary safety endpoint “proportion of patients with ocular adverse events” over the on-treatment period please refer to [Section 7.3.4](#).

### 7.3.2 Secondary endpoint analyses

The proportion of patients with at least 2 steps improvement from baseline on the DRSS ([Table 10.3: 1](#)) in the study eye at week 12 will be summarized as the frequency and percentage of patients. Logistic regression analyses adjusted for treatment and baseline visual acuity may be performed if a sufficient number of events is observed. Baseline measurements are defined in [Section 5.1](#). The odds ratio and corresponding 95% confidence interval will be presented along with the p-value. The analysis will be performed on the FAS.

For analyses of the secondary safety endpoint “proportion of patients with adverse events other than ocular adverse events” over the on-treatment period, refer to [Section 7.3.4](#).

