Main in- and exclusion criteria	Male or female patients; of legal age Diagnosis of diabetes mellitus Type 1 or Type 2 Non-proliferative diabetic retinopathy (NPDR) without CI-DME in the study eye at screening with NPDR level 47 or level 53, as determined by the Central reading center (CRC) by using the DRSS Best corrected visual acuity Early Treatment Diabetic Retinopathy Study (ETDRS) letter score $\geq$ 70 letters in the study eye at screening No evidence of active neovascularization of the iris or angle neovascularization in the study eye No prior pan-retinal photocoagulation in the study eye No history of Diabetic macular edema (DME) or DR treatment with macular laser within 3 months prior to screening, or intraocular injections of medication within 6 months prior to screening, and no more than 4 prior intraocular injections at any time in the past in the study eye
Test product:	BI 1467335 film-coated tablets
dose:	10 mg daily (two 5 mg tablets q.d.)
mode of administration:	p.o.
Comparator products:	Placebo film-coated tablets
dose:	Not applicable
mode of administration:	p.o.
Duration of treatment:	12 weeks of treatment with 12 weeks follow-up
Endpoints:	Primary endpoint is the proportion of patients with ocular adverse events according to Common Terminology Criteria for Adverse Events (CTCAE) over the on-treatment period (over 24 weeks). Secondary endpoints are the proportion of patients with at least 2 steps improvement in the study eye on the DRSS at week 12 compared to baseline, and the proportion of patients with adverse events (according to CTCAE) other than ocular adverse events over the on-treatment period (over 24 weeks)
Safety criteria:	Adverse event reporting, vital signs, 12-lead electrocardiogram (ECG) and standard safety laboratory parameters.
Statistical methods:	The randomization will be stratified by the severity level of the disease under study as assessed by DRSS, i.e. levels 47 or 53. Endpoints related to proportion of patients with improvement in DRSS will be summarized descriptively and will be analyzed using logistic regression adjusting for baseline visual acuity if sufficient numbers of events are observed..  All other endpoints will be analyzed using descriptive statistics.

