#### 3.2 DISCUSSION OF TRIAL DESIGN, INCLUDING THE CHOICE OF CONTROL GROUP(S)

A randomized, double-masked placebo-controlled design is chosen for this trial in order to evaluate safety, tolerability, pharmacokinetics and pharmacodynamics of 10 mg q.d. of BI 1467335 in patients with moderately severe NPDR (DRSS level 47) or severe NPDR (DRSS level 53) without CI-DME. Because currently there is no efficacious therapy available

for this patient group at this stage of the disease, this trial aims to improve the level of disease severity at early time points in the course of the disease.

The treatment period of 12 weeks is deemed adequate to evaluate safety and tolerability, and is covered by currently available toxicology data.

A placebo control arm was chosen for this trial in order to compare BI 1467335 and placebo regarding safety and tolerability in patients with NPDR. Approximately equal numbers of patients will be randomized to both treatment groups. Randomization will be stratified by the level of disease severity (please refer to [Section 7](#)) based on DRSS levels 47 or 53 as this may have impact on the expected effects regarding the primary outcome.

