## 7. STATISTICAL METHODS AND DETERMINATION OF SAMPLE SIZE

### 7.1 STATISTICAL DESIGN - MODEL

The trial is a randomized, double-masked, placebo-controlled, parallel-group, multicenter proof of clinical principle study. The primary objective is to evaluate the safety and tolerability of BI 1467335 and to explore the mechanism of BI 1467335 in the treatment of patients with moderately severe NPDR (DRSS level 47) or severe NPDR (DRSS level 53), without CI-DME.

BI 1467335 will be compared to placebo. The primary endpoint is occurrence of ocular adverse events.

The randomization will be stratified by the severity level of the disease under study as assessed by DRSS, i.e. level 47 or 53.

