7.5.2 Secondary endpoint(s)

[figure not shown]
The frequency and percentage of patients in the FAS with at least 2 steps improvement from baseline on the DRSS, as defined in [Table 5.2.2: 1](#), in the study eye at week 12 will be summarized by treatment. Baseline DRSS is the value recorded at Visit 2a. If DRSS is not

Proprietary confidential information © 2020 Boehringer Ingelheim International GmbH or one or more of its affiliated companies

[figure not shown]
measured at Visit 2a, baseline DRSS is the value recorded at Visit 1. The frequency of patients reporting improvement in DRSS of at least 2 steps is expected to be low. The risk difference and corresponding 95% confidence intervals calculated using the method of Chan and Zhang ([7](#)) will be reported.

[figure not shown]
In addition, a shift table showing the frequency and percentage of patients reporting each Week 12 DRSS by baseline DRSS value will be presented. A visual display of the percentage of patients experiencing no change from baseline, a one-step and two-step improvement in DRSS from baseline to Week 12 or one-step worsening will be created. Similar summaries will be prepared using DRSS data collected from the non-study eye.

[figure not shown]
If a sufficient number of patients report improvement of 2 steps or more in the study eye, logistic regression analyses adjusted for visit, treatment and baseline visual acuity will be performed as exploratory analyses. The resulting odds ratios at each time point and corresponding 95% confidence interval will be presented, if modeling is possible.

Additionally, analyses described in this section will be repeated using the PPS instead of the FAS.

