- Drug-related SAEs
- AEs leading to death
- AEs of special interest (AESI)
- Other significant AEs according to ICH E3 ([13](#)).

Per CTP Section 5.2.6.1.4, AESIs for this trial are events of hepatic injury defined by an elevation of AST and/or ALT ≥ 3 fold upper limit of normal (ULN) combined with an elevation of bilirubin ≥ 2 fold ULN measured in the same blood draw, or aminotransferase (ALT and/or AST) elevations ≥ 10 fold ULN. AEs related to these definitions will be summarized as AESIs.

Additionally, a table summarizing time to first AE from date of first dose of study drug will be presented by treatment arm, SOC and preferred term.

Primary endpoint: Ocular AEs

In addition to standard adverse event tables, separate summaries will be provided to address the primary endpoint and secondary safety endpoints. The frequency and percentage of patients reporting ocular AEs, as identified by the investigator as an ocular event on the AE eCRF, will be summarized by treatment, highest CTC grade, primary SOC, and PT for the primary endpoint analysis. The number and percentage of patients in each treatment arm

reporting specific ocular symptoms will be summarized and will be displayed by associated event in a listing. Additional summaries of serious ocular AEs, drug-related ocular AEs, serious drug-related ocular AEs, and ocular AEs leading to discontinuation will be provided, if any such events are reported. A Kaplan-Meier plot displaying time to first ocular event following first dose of study drug will be provided.

To assess the impact of the COVID-19 pandemic on this trial, adverse events reported after 01MAR2020 in the subset of patients active in the trial as of 01MAR2020 will be reported and listed in the CTR. Overall summaries of the subset of all AEs and subset of ocular AEs with start dates prior to 01MAR2020 will be reported separately. In addition, frequencies of AEs reported during the follow-up period will be reported in the subset of patients who completed the trial prior to 01MAR2020 and in the subset of patients who completed the trial after 01MAR2020.

Secondary endpoint: Non-ocular AEs

A separate set of the tables specified above for ocular AEs will be generated to summarize patients reporting AEs not identified as ocular AEs. These summaries will address the analysis of the secondary safety endpoint. The data will be summarized by treatment, MedDRA primary SOC, and PT.

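### Minor, nearly free improvement: randomisation is stratified by DRSS 47/53, but in the readable text neither the conditional logistic model nor the ocular-AE summary uses the stratum

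*Protocol*

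**What the plan says.** **Randomisation.** Protocol 7.1 states: "The randomization will be stratified by the severity level of the disease under study as assessed by DRSS, i.e. level 47 or 53". Protocol 3.2 gives the reason, describing the stratification as "based on DRSS levels 47 or 53 as this may have impact on the expected effects regarding the primary outcome". The primary outcome is the proportion of patients with ocular AEs (Protocol 2.1.2).

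**Two-step DRSS improvement.** Protocol 7.3.2 says "Logistic regression analyses adjusted for treatment and baseline visual acuity may be performed", conditional on a sufficient number of events. The synopsis says such endpoints "will be analyzed using logistic regression adjusting for baseline visual acuity if sufficient numbers of events are observed". SAP 7.5.2 says that, on the same kind of condition, "logistic regression analyses adjusted for visit, treatment and baseline visual acuity will be performed" as exploratory analyses. None of the three names the DRSS stratum. The main result in SAP 7.5.2 is by treatment: "The risk difference and corresponding 95% confidence intervals calculated using the method of Chan and Zhang". The same section adds that "a shift table showing the frequency and percentage of patients reporting each Week 12 DRSS by baseline DRSS value will be presented".

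**Ocular AEs.** SAP 7.8.1 says the frequency and percentage of patients "will be summarized by treatment, highest CTC grade, primary SOC, and PT for the primary endpoint analysis". It adds a Kaplan-Meier plot of time to first ocular event. No readable ocular-AE display is split by DRSS level.

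**What limits the point.** Protocol 7.2 plans no confirmatory testing and Protocol 7.3.4 makes safety analysis descriptive. Protocol 7.3.3, SAP 6.4 and the SAP section between 7.5 and 7.7 are not readable.

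**The concern.** A stratification factor is normally carried into the analysis, because the comparison then follows the groups within which patients were allocated. Here the plan chose one factor and gave a reason for it that refers to the primary outcome. In the readable text, though, the only baseline covariate in the efficacy model is visual acuity, and the primary endpoint is not displayed by the factor at all.

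What is at stake is modest. A reader who knows why the trial was stratified will want to see ocular AEs by stratum and arm, and will expect any fitted model to include the stratum. No type I error rate, power or sample size depends on it.

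**Working it through.** **1. The plan's own figure.** Protocol 7.7 assumes 6% response on active and 0% on placebo, with 50 patients per arm, and gives about 80% for seeing 2 responders. Reading this as at least 2 of 50 active patients:

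P(X ≥ 2) = 1 − 0.94^50 − 50 × 0.06 × 0.94^49 = 1 − 0.045 − 0.145 = 0.810.

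The figure reproduces. It does not involve the model, so the stratum cannot change it.

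**2. How often the model would be run.** Expected responders are 50 × 0.06 = 3, in line with SAP section 4, which expects no more than 3. For Binomial(50, 0.06), P(X ≥ 5) = 0.18 and P(X ≥ 10) = 0.0007. With no placebo responders the ordinary treatment odds ratio has no finite estimate, with or without the stratum.

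**3. Main result.** At 3/50 against 0/50, the Chan-Zhang 95% interval is about −1.4 to 16.4 percentage points. It is calculated from the two arms only, so it stays as it is.

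**4. Effect of the stratum when the model can be run.** Assumptions: 8/50 against 2/50 responders, 25 patients per arm per stratum, one time point, terms for treatment and stratum only (visual acuity and visit not modelled). z = ln(OR) / SE. Without the stratum, OR = (8 × 48) / (42 × 2) = 4.57, SE = √(1/8 + 1/42 + 1/2 + 1/48) = 0.818 and z = 1.86. With the stratum:

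| Active responders, 47 / 53 | Placebo responders, 47 / 53 | OR | SE of log OR | z |
|---|---|---|---|---|
| 4 / 4 | 1 / 1 | 4.57 | 0.818 | 1.86 |
| 2 / 6 | 1 / 1 | 4.69 | 0.824 | 1.88 |
| 2 / 6 | 0 / 2 | 4.85 | 0.832 | 1.90 |
| 1 / 7 | 0 / 2 | 5.08 | 0.841 | 1.93 |

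The standard error rises slightly, but so does the log odds ratio, and z never falls.

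**5. When adding the stratum is unsafe.** With 3 responders, all in an active arm split 25/25, and no effect of level, the chance that all fall in one stratum is 2 × C(25,3) / C(50,3) = 2 × 2,300 / 19,600 = 0.23. The stratum coefficient then has no finite estimate in an ordinary fit.

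**6. Ocular AEs.** The documents give no rate, so these are assumptions, with 25 per arm per stratum. The unstratified SE of the risk difference is √[(p̄₁(1 − p̄₁) + p̄₀(1 − p̄₀)) / 50]. The stratified SE is √[Σ 0.25 × (p₁(1 − p₁) + p₀(1 − p₀)) / 25], summed over strata.

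- Equal rates of 20% in both strata: 0.0800 and 0.0800, ratio 1.00.
- Stratum rates 10% and 30% in both arms: 0.0800 and 0.0775, ratio 0.97.
- Placebo 15% and 45%, active 15 points higher: 0.0957 and 0.0908, ratio 0.95.

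Stratifying would therefore narrow the standard error by about 0 to 5%. Single cells remain imprecise: the exact 95% interval is 0 to 13.7% for 0/25 and 2.5 to 31.2% for 3/25.

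**The case against.** The strongest reply is that nothing is broken. The trial is exploratory, safety is descriptive and no stratified analysis is promised anywhere. Protocol 3.2 says only that the level may matter, which is a reason to balance allocation, and stratified randomisation has already done that. All of this stands, and it is why the point is an improvement and not an error.

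Three narrower objections also carry weight:

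- **Model instability.** Adding the stratum every time the model is run would be unsafe with few events, as step 5 shows, and the plan does not define a sufficient number of events. The fix is therefore conditional.
- **Responders by level.** The shift table in SAP 7.5.2 already shows Week 12 DRSS by baseline DRSS, so a separate responder table is not needed. The match may not be exact. The shift table uses the Visit 2a grade when available, while the stratum probably rests on the screening grade. That is an inference from Protocol 6.2.1; no passage says which grade the randomisation system uses.
- **Interpretation of the AE table.** Levels 47 and 53 describe the study eye (Protocol 3.3.1), whereas both eyes are examined (Protocol 5.1) and ocular AEs are counted per patient. The table needs a footnote.

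A further objection is that adding the stratum raises the standard error of the log odds ratio. Taken alone this misleads, because the estimate moves with it and z does not fall.

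**Conclusion.** The point holds as a minor improvement. In the readable text, the one stratification factor is absent from the conditional logistic model and from the ocular-AE summary. The benefit is small: z rises from 1.86 to at most 1.93 in the assumed 8/50 against 2/50 scenarios, and the ocular-AE standard error would fall by 0 to 5% at the assumed rates. At the planned response rates the model will rarely be run. The ocular-AE table is the more useful half, since it addresses the outcome named in the reason for stratifying.

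These sizes assume equal strata and, for ocular AEs, rates that the documents do not give.

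A reader might infer that the plan contradicts itself, or that its intervals are invalid because the stratum is left out. The documents support neither reading. No passage commits to a stratified analysis, no confirmatory test is planned, and the Chan-Zhang comparison of the two arms remains a sound main result. Nor can it be said that no stratum display exists, because parts of both documents are redacted.

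**What to change.** 1. **SAP 7.5.2.** When there are enough events to run the logistic model, include the DRSS 47/53 randomisation stratum alongside baseline visual acuity. Require responders in both arms and in both strata; otherwise use a penalised (Firth) or exact fit. Keep the unstratified Chan-Zhang interval as the main result. Do not add a separate responder table.
2. **SAP 7.8.1.** Add one descriptive table of patients with ocular AEs by randomisation stratum and arm. Footnote that the stratum is the study-eye level while the events may arise in either eye.

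**Cost.** One SAP line and one small table, with no new patients or assessments; the stratum should already be in the randomisation record (assumption). Cells hold about 25 patients if the strata are equal, so the table must be labelled descriptive and not read as a stratum effect. The SAP history table marks the document as final before database lock, so the change needs a dated update before unmasking; made later, it should be labelled post hoc.

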### 7.3.4 Safety analyses

All findings noticed at ophthalmological examinations and/or clinically relevant symptoms (according to the judgment of the investigator) which are reported by the patients will be recorded as ocular adverse events according to the CTCAE classification. All adverse events will be coded using the Medical Dictionary for Drug Regulatory Activities (MedDRA).

Standard BI summary tables and listings will be produced. Consistent with the REP definition in [Section 5.2.6.2.1](#), all adverse events with an onset between start of treatment and last follow up visit will be assigned to the on-treatment period for evaluation. Measurements (such as ECG, vital signs, or laboratory parameters) or AEs will be assigned to treatments (see [Section 4.1](#)) based on the actual treatment at the planned time of the measurement or on the recorded time of AE onset (concept of treatment emergent AEs). Therefore, measurements planned or AEs recorded prior to first intake of trial medication will be assigned to 'screening' and those between first trial medication intake until the last follow up visit will be assigned to the treatment period. These assignments including the corresponding time intervals will be defined in detail in the TSAP.

All treated patients will be included in the safety analysis. In general, safety analyses will be descriptive in nature and will be based on BI standards. No hypothesis testing is planned.

Statistical analysis and reporting of adverse events will concentrate on treatment-emergent adverse events, i.e. all adverse events occurring between start of treatment and last follow up visit. Adverse events that start before first drug intake and deteriorate under treatment will also be considered as 'treatment-emergent'.

Frequency, severity, and causal relationship of adverse events will be tabulated by system organ class and preferred term after coding according to the current version of the Medical Dictionary for Drug Regulatory Activities (MedDRA) at the database lock. This also includes the primary endpoint.

Laboratory data will be analyzed both quantitatively as well as qualitatively. The latter will be done via comparison of laboratory data to their reference ranges. Values outside the reference range as well as values defined as clinically relevant will be summarized. Treatment groups will be compared descriptively with regard to distribution parameters as well as with regard to frequency and percentage of patients with abnormal values or clinically relevant abnormal values.

Clinically relevant ECG findings will be reported as baseline conditions or AEs. Quantitative and qualitative ECG data from the ECG reading center will be reported descriptively.

Vital signs, physical examinations, or other safety-relevant data observed at screening, baseline, during the course of the trial and at the end-of-trial evaluation will be assessed with regard to possible changes compared to findings before start of treatment.

[REDACTED]

[REDACTED]

[REDACTED]

#### 7.4 INTERIM ANALYSES

[REDACTED]

During the conduct of the interim analysis, access to unmasked data will be restricted to members of the trial and project teams not directly involved with study conduct. The results of the interim analysis will not be used to make any adaptations of this trial, like sample size adjustments.

For steps to maintain blinding during the interim analysis see [Section 4.1.5.1](#).

#### 7.5 HANDLING OF MISSING DATA

For the analyses of efficacy endpoints, if a patient misses a visit, the missing data will not be imputed and only on-treatment data will be included.

Additional details on the handling of missing data, including sensitivity analyses of the efficacy endpoints and any imputation rules for further endpoints will be specified in the TSAP prior to unmasking. No imputation is planned for the analysis of AEs, laboratory data or vital signs. Rules for handling missing data are outlined in BI SOPs.

#### 7.6 RANDOMISATION

BI will arrange for the randomization and the packaging and labelling of trial medication. The randomization list will be generated using a validated system, which involves a pseudo-random number generator so that the resulting treatment will be both reproducible and non-predictable. The block size will be documented in the CTR. Access to the codes will be controlled and documented. Procedural aspects of assigning patients to treatment groups and controlling the randomization code are provided in [Section 4.1.3](#) and [Section 4.1.5](#).

#### 7.7 DETERMINATION OF SAMPLE SIZE

The primary endpoint for the trial is occurrence of ocular adverse events.

As this is an exploratory study, no formal sample size calculation has been applied. It is expected that using 50 patients per group will be sufficient to detect clinically relevant signals for ocular events between active treatment and placebo.

Additionally, with DRSS data from 100 patients the probability of seeing at least 2 steps improvement in the study eye on the DRSS at week 12 compared to baseline in 2 patients is approximately 80%, assuming a response rate of 6% on active treatment and 0% response on placebo.

[figure not shown]

Figure 7.7: 1 Probabilities for seeing different amount of patients with 2 step improvement in DRSS assuming different success rates.

